7.2. Study Rationale

This is the first study of OMS721 in subjects with complement-associated nephropathies, including IgAN, lupus nephritis, MN, and C3 glomerulopathy including dense deposit disease. The study is designed to evaluate whether OMS721 may improve renal function and/or reduce corticosteroid needs in subjects with these nephropathies. Each of these diseases has glomerular inflammation and evidence of lectin pathway activation. Persistent renal inflammation is

CONFIDENTIAL

No use, disclosure or reproduction outside of Omeros without prior written authorization

associated with progressive deterioration in renal function. Treatment often involves chronic corticosteroids and many patients require high-dose corticosteroids. Many patients have serious long-term adverse consequences on chronic high-dose corticosteroid treatment. OMS721 may improve proteinuria, which is associated with improved outcomes, and decrease the corticosteroid needs.

Measurement of urinary protein or albumin is routinely used to assess kidney involvement and persistent high levels of urinary protein correlate with disease progression. The 24-hour urine protein is used clinically to assess proteinuria and has been demonstrated to be predictive of outcome in patients with IgAN.

Results from nonclinical toxicity and clinical studies of OMS721 indicate that there is an adequate safety margin to conduct this study at the proposed dose in subjects with complement-associated kidney diseases. Subjects treated to date have tolerated OMS721 treatment well.

Cohort 3 is being added to ensure that all subjects may receive active therapy if they have significant proteinuria following treatment with blinded study drug. Also, because continued suppression of urinary protein has been observed in IgAN subjects treated with OMS721, subjects in Cohort 3 will undergo extended follow-up to determine the duration of the urine protein suppression. Subjects may receive open-label OMS721 treatment if they do not achieve a therapeutic response with the initial 12-week blinded study drug treatment course or if their urinary protein increases after achieving a therapeutic response. Chronic toxicology has been completed and supports indefinite dosing. Follow-up through 24 months with visits approximately every 13 weeks will allow assessment of duration of therapeutic response with minimal burden to subjects. Subjects with IgAN in Cohort 1 and subjects in Cohort 2 who have not completed the study may roll into Cohort 3 to be able to receive extended OMS721 treatment.

Asian subjects with IgAN residing in Asia have been added to provide initial evaluation of OMS721 in this population. The literature reports that IgAN in the Asian population may be more severe due to genetic or environmental conditions [Magistrini 2015].

7.2.1. Rationale for Dose Selection

The dose level of OMS721 370 mg IV in this study inhibits the lectin pathway for approximately one week and provides high levels of lectin pathway inhibition for approximately 4 to 5 days. Prior doses of 4 mg/kg were associated with marked improvement in urinary protein measures in subjects with aHUS, IgA nephropathy, MN, and lupus nephritis. This dose was well tolerated. The fixed dose is within the range of doses provided previously in this study.

7.3. Study Endpoints

7.3.1. Primary Endpoints

The primary endpoints are:

- Safety and tolerability of OMS721 as assessed by AEs, vital signs, clinical laboratory tests, and ECGs

7.3.2. Secondary Endpoint

The secondary endpoints are:

- Proteinuria from baseline to 12 weeks assessed by 24-hour urine protein collection by disease
- Urine albumin/creatinine ratio by disease
- Corticosteroid dose needed to maintain stable renal function by disease (Cohort 1)
- PK
- PD

7.3.3. Exploratory Endpoint

The exploratory endpoints are:

- Urine protein/creatinine ratio by disease
- Serum creatinine by disease
- eGFR by disease calculated by the MDRD equation, the CKD-EPI equation using serum creatinine, the CKD-EPI equation using cystatin C, and the CKD-EPI equation using creatinine – cystatin C
- Occurrence of ADA and NAb
- Urine inflammatory markers by disease
- Duration of therapeutic response, if observed, defined as the number of consecutive weeks that 24-hour urine protein < 50% of baseline for up to 104 weeks (Cohort 3 only)

8. SELECTION AND WITHDRAWAL OF SUBJECTS

8.1. Subject Inclusion Criteria

Subjects may be included in the study only if they meet all of the following criteria:

1. Competent to provide informed consent.
2. Voluntarily provide informed consent in accordance with regulations and governing institutional review board (IRB) or independent ethics committee (IEC) requirements prior to any procedures or evaluations performed specifically for the sole purpose of the study.
3. Are age ≥ 18 years at Screening Visit 1.
4. Have a diagnosis of one of the following:
 - IgAN diagnosed on kidney biopsy
 - Lupus nephritis diagnosed on kidney biopsy (Cohort 1 only)

CONFIDENTIAL

No use, disclosure or reproduction outside of Omeros without prior written authorization

- Primary MN diagnosed on kidney biopsy (Cohort 1 only)
 - C3 glomerulopathy including dense deposit disease diagnosed on kidney biopsy (Cohort 1 only)
5. Have 24-hour urine protein > 1000 mg/24 hours.
 6. For subjects in Cohort 1, have been on ≥ 10 mg of prednisone or equivalent dose for at least 12 weeks prior to Screening Visit 1.
 7. If on immunosuppressive treatment (e.g., cyclophosphamide, mycophenolate mofetil), have been on a stable dose for at least 2 months prior to Screening Visit 1 with no expected change in the dose for the study duration.
 8. Have an eGFR ≥ 30 mL/min/1.73 m² calculated by the MDRD equation.
 9. Are on physician-directed, stable, optimized treatment with ACEIs and/or ARBs and have a systolic blood pressure of < 150 mmHg and a diastolic blood pressure of < 90 mmHg at rest.
 10. If female, are either a) not of childbearing potential (i.e., surgically sterilized or postmenopausal for > 1 year), b) have a negative pregnancy test and if sexually active must agree to use two medically reliable forms of contraception throughout the study, or c) have a medically sterilized male partner. Acceptable methods of contraception include a reliable intrauterine device, hormonal contraception, or a barrier method.
 11. If male, are either a) not of reproductive potential or b) if sexually active must agree to use a medically reliable form of contraception throughout the study. Acceptable methods of birth control include spermicide in combination with a barrier method, or subject's female partner is willing to use medically acceptable methods of birth control (intrauterine device, hormonal contraception, or a barrier method).

8.2. Subject Exclusion Criteria

Subjects will be excluded from the study for any of the following reasons:

1. Have a known hypersensitivity to any constituent of the investigational product.
2. Have a hemoglobin < 9.0 g/dL.
3. Have a platelet count < 100,000/mm³.
4. Have an absolute neutrophil count < 500 cells/mm³.
5. Have an ALT or AST > 3.0 x the upper limit of normal.
6. Have systemic manifestations of Henoch-Schonlein purpura (e.g., joint pain, gastrointestinal bleeding, abdominal pain) within 2 years prior to Screening Visit 1.
7. Have used belimumab, eculizumab, or rituximab within 6 months of Screening Visit 1.
8. Have a history of renal transplant.
9. Have a diagnosis of human immunodeficiency virus (HIV), hepatitis B, or hepatitis C infection or positive serology at Screening Visit 1 for HIV, hepatitis B, or hepatitis C.

CONFIDENTIAL

No use, disclosure or reproduction outside of Omeros without prior written authorization

10. Have any significant infection requiring antibiotic treatment at Screening Visit 1.
11. Have a malignancy except for adequately treated and cured basal or squamous cell skin cancer, curatively treated *in situ* disease, or other cancer from which the patient has been disease-free for ≥ 5 years.
12. Have an expectation of survival of less than 24 months.
13. If female, are pregnant or breastfeeding.
14. Have received any other investigational drug or device or experimental procedures within 30 days of Screening Visit 1.
15. Are an employee of Omeros, the investigative site, a study staff member, or their immediate family member.
16. Have any condition that the Investigator believes would put the subject at risk from participation.
17. For subjects in Cohort 2 and Cohort 3, have received corticosteroids within the 3 months prior to screening. Subjects in Cohort 1 rolling into Cohort 3 must have IgAN and must have discontinued corticosteroids prior to entry into Cohort 3, but the discontinuation may occur at any time prior to Cohort 3 entry.

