Clinic visits for subjects in Cohort 1 and Cohort 2 will occur at screening, weekly through the treatment period, and 1, 4, and 6 weeks following the last dose of study drug. Cohort 1 and Cohort 2 subjects will be in the study for approximately 22 weeks.

Clinic visits for subjects in Cohort 3 will occur at screening, weekly through the treatment period and 1, 4, and 6 weeks following the 12th blinded study drug dose at Week 12. Cohort 3 subjects who have 24-hour urine protein < 500 mg will enter the follow-up period with visits at weeks 26, 39, 52, 65, 78, 91 and 104. Cohort 3 subjects who have 24-hour urine protein > 1000 mg or 24-hour urine protein $\geq 50\%$ of baseline anytime between weeks 18-91 during the follow-up period may elect, with the agreement of the Investigator, to receive open-label OMS721 370 mg IV once weekly for 12 weeks. Additional 12-week OMS721 treatment courses may be administered as often as subjects have 24-hour urine protein > 1000 mg or 24-hour urine protein $\geq 50\%$ of baseline during weeks 18-91. Subjects in Cohort 3 will be in the study approximately 25 months.

In Cohort 3, data analyses will be performed after the 6-week follow-up period of the initial 12 weeks of study drug treatment for both the exclusive Asian and non-exclusive Asian groups.

Clinical and laboratory assessments will be done at each study visit.

Number of Subjects (Planned): Approximately 44 (approximately 16 in Cohort 1, approximately 10 in Cohort 2, and approximately 18 in Cohort 3)

CONFIDENTIAL

No use, disclosure or reproduction outside of Omeros without prior written authorization

Inclusion Criteria:

Subjects may be included in the study only if they meet all of the following criteria:

1. Competent to provide informed consent.
2. Voluntarily provide informed consent in accordance with regulations and governing institutional review board (IRB) or independent ethics committee (IEC) requirements prior to any procedures or evaluations performed specifically for the sole purpose of the study.
3. Are age ≥ 18 years at the Screening Visit 1.
4. Have a diagnosis of one of the following:
 - IgAN diagnosed on kidney biopsy
 - Lupus nephritis diagnosed on kidney biopsy (Cohort 1 only)
 - Primary MN diagnosed on kidney biopsy (Cohort 1 only)
 - C3 glomerulopathy including Dense Deposit Disease diagnosed on kidney biopsy (Cohort 1 only)
5. Have 24-hour urine protein > 1000 mg/24 hours.

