6. For subjects in Cohort 1, have been on ≥ 10 mg of prednisone or equivalent dose for at least 12 weeks prior to Screening Visit 1.
7. If on immunosuppressive treatment (e.g., cyclophosphamide, mycophenolate mofetil), have been on a stable dose for at least 2 months prior to Screening Visit 1 with no expected change in the dose for the study duration.
8. Have an eGFR ≥ 30 mL/min/1.73 m² calculated by the MDRD equation.
9. Are on physician-directed, stable, optimized treatment with angiotensin converting enzyme inhibitors (ACEI) and/or angiotensin receptor blockers (ARB) and have a systolic blood pressure of < 150 mmHg and a diastolic blood pressure of < 90 mmHg at rest.
10. If female, are either a) not of childbearing potential (i.e., surgically sterilized or postmenopausal for > 1 year), b) have a negative pregnancy test and if sexually active must agree to use two medically reliable forms of contraception throughout the study, or c) have a medically sterilized male partner. Acceptable methods of contraception include a reliable intrauterine device, hormonal contraception, or a barrier method.
11. If male, are either a) not of reproductive potential or b) if sexually active must agree to use a medically reliable form of contraception throughout the study. Acceptable methods of birth control include spermicide in combination with a barrier method, or subject's female partner is willing to use medically acceptable methods of birth control (intrauterine device, hormonal contraception, or a barrier method).

CONFIDENTIAL

No use, disclosure or reproduction outside of Omeros without prior written authorization

Exclusion Criteria:

1. Have a known hypersensitivity to any constituent of the investigational product.
2. Have a hemoglobin < 9.0 g/dL.
3. Have a platelet count < 100,000/mm³.
4. Have an absolute neutrophil count < 500 cells/mm³.
5. Have an alanine transaminase (ALT) or aspartate transaminase (AST) > 5.0 x the upper limit of normal.
6. Have systemic manifestations of Henoch-Schonlein purpura (e.g., joint pain, gastrointestinal bleeding, abdominal pain) within 2 years prior to Screening Visit 1.
7. Have used belimumab, eculizumab, or rituximab within 6 months of Screening Visit 1.
8. Have a history of renal transplant.
9. Have a diagnosis of human immunodeficiency virus (HIV), hepatitis B, or hepatitis C infection, or positive serology at Screening Visit 1 for HIV, hepatitis B, or hepatitis C.

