10. Have any significant infection requiring antibiotic treatment at Screening Visit 1.
11. Have a malignancy except for adequately treated and cured basal or squamous cell skin cancer, curatively treated in situ disease, or other cancer from which the patient has been disease-free for ≥ 5 years.
12. Have an expectation of survival of less than 24 months.
13. If female, are pregnant or breastfeeding.
14. Have received any other investigational drug or device or experimental procedures within 30 days of Screening Visit 1.
15. Are an employee of Omeros, the investigative site, a study staff member, or their immediate family member.
16. Have any condition that the Investigator believes would put the subject at risk from participation.
17. For subjects in Cohort 2 and Cohort 3, have received corticosteroids within the 3 months prior to screening. Subjects in Cohort 1 rolling into Cohort 3 must have IgAN and must have discontinued corticosteroids prior to entry into Cohort 3, but the discontinuation may occur at any time prior to Cohort 3 entry.

Investigational Product, Dosage, and Mode of Administration:

[REDACTED]

[REDACTED]

[REDACTED]

Duration of Treatment: 12 weeks for Cohorts 1 and 2; Initially 12 weeks with potential additional treatment for Cohort 3

CONFIDENTIAL

No use, disclosure or reproduction outside of Omeros without prior written authorization

Reference Therapy, Dosage, and Mode of Administration: Intravenous D5W for Cohort 2 and 3 only

Study Endpoints:

1. Safety and tolerability of OMS721 as assessed by AEs, vital signs, clinical laboratory tests, and ECGs
2. Change from baseline in 24-hour urine protein
3. Change from baseline in urine albumin/creatinine ratio by disease
4. Corticosteroid dose required to maintain stable renal function by disease (Cohort 1)

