7. STUDY DESIGN AND PROCEDURES

7.1. Summary of Study Design

This is a Phase 2, multicenter study of OMS721 in subjects with the following diseases: IgAN, lupus nephritis, MN, or C3 glomerulopathy including dense deposit disease. Three cohorts will be enrolled:

- Cohort 1 will be subjects with corticosteroid-dependent IgAN, LN, MN, or C3 glomerulopathy. All Cohort 1 subjects will be receiving a corticosteroid dose of ≥ 10 mg of prednisone or equivalent dose for at least 12 weeks. Cohort 1 subjects will all receive OMS721 4 mg/kg intravenously (IV) once weekly for 12 weeks.
- Cohort 2 will be subjects with IgA nephropathy who are not receiving corticosteroids. Cohort 2 subjects will receive either OMS721 4 mg/kg IV treatment or 5% dextrose in water (D5W) vehicle once weekly for 12 weeks in a randomized double blind design.
- Cohort 3 will be subjects with IgA nephropathy who are not receiving corticosteroids. Subjects in Cohort 3 will receive either OMS721 370 mg IV or 5% dextrose in water (D5W) vehicle in a randomized double blind design. Regardless of treatment assignment, subjects in Cohort 3 will be eligible for additional open-label OMS721 treatment if they fail to achieve a 24-hour urine protein $< 50\%$ of baseline or their 24-hr urine protein is $> 1000\text{mg}/24\text{-hours}$ after 12 weeks of dosing [plus a 6-week follow-up period].

Cohorts 1 and 2 are ongoing at the time of this amendment. Upon approval of this amendment, subjects with IgAN in Cohort 1 and subjects in Cohort 2 who have started study drug and are on study will be offered the opportunity to roll into Cohort 3 for extended treatment and long-term follow-up. Subjects have to sign an informed consent and meet the eligibility criteria in order to participate in Cohort 3. The rollover subjects will not be randomized and will receive open-label OMS721 370 mg IV once per week for the remaining treatment period of their original cohort. Following rollover they will follow all study procedures for Cohort 3. Subjects with IgAN in Cohort 1 must have discontinued corticosteroids in order to roll into Cohort 3. Subjects with LN, MN or C3 glomerulopathy in Cohort 1 are not eligible rollover into Cohort 3.

Approximately 44 subjects will be enrolled (16 in Cohort 1, 10 in Cohort 2, and 18 in Cohort 3) from up to approximately 15 investigative sites.

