10.1. Study Schedule

10.1.1. Screening Visit 1 (within 28 days of the first dose)

Screening evaluations will occur on two separate occasions within 28 days prior to dosing (Day 1). Before any of the screening evaluations are performed for the specific purpose of this study, the subject must provide informed consent for this study in compliance with regulations and governing IRB/IEC requirements. A subject is considered enrolled into the study once they have provided informed consent and have been assigned a subject number.

The subjects who have begun or completed Screening in Cohort 2 but have not received the first dose must sign an informed consent form and transfer into Cohort 3 prior to randomization. The

duration of the screening period for these subjects is up to 90 days. No screening procedures need to be repeated except a single 24-hour urine protein to be provided within 7 days prior to the first dose of study drug if the subject's screening 24-hour urine protein was provided more than 21 days prior to the first dose of study drug.

During Screening Visit 1, the procedures listed below will be performed and documented to determine subject eligibility prior to treatment assignment.

1. A medical history and demographic information including obtaining a history of whether a patient is anti-PLA-2R antibody positive for subjects with a history of MN.
2. Use of prior and concomitant medications, including corticosteroid dose (if applicable).
3. Vital signs including BP, pulse rate, respiratory rate (RR) and temperature (after at least 5 minutes of rest).
4. A physical examination, including height and weight. Examination of breast, rectal, and genitourinary systems may be deferred unless clinically necessary.
5. A 12-lead ECG (after at least 5 minutes of rest in the supine position).
6. Clinical laboratory tests for hematology, chemistry, coagulation, cystatin C, urinalysis, urine for inflammatory biomarkers, and anti-PLA-2R antibody in subjects with MN. See Section 12.1.1 for complete list required laboratory assessments.
7. Serum pregnancy testing in women of childbearing potential.
8. Serology tests for HIV, hepatitis B, and hepatitis C.

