9. The subject will be instructed to collect urine samples for albumin/creatinine and protein/creatinine ratios on any 3 consecutive days prior to their next screening visit (i.e., a total of two three-consecutive-day collections during screening). Dispense appropriate supplies for the urine collection. NOTE: all samples for urine albumin/creatinine and protein/creatinine ratios must be collected at first void in the morning and kept in the refrigerator until the subject returns them.
10. The subject will be instructed to collect urine for 24-hour urine protein excretion and appropriate supplies will be provided. The subject will be instructed to perform the urine collection and return to the clinical site at Screening Visit 2. Subjects must return the urine to the site within 3 days of collection to prevent degradation of the sample.

10.1.2. Screening Visit 2 (At least 7 days after Screening Visit 1 and approximately 7 days prior to Treatment Visit 1)

At Screening Visit 2 the following will be performed and documented:

1. Collect urine samples from Screening Visit 1.
2. The subject will be instructed to collect additional urine samples for albumin/creatinine and protein/creatinine ratios on 3 consecutive days prior to Treatment Visit 1. Dispense appropriate supplies for the urine collection. NOTE: all samples for urine albumin/creatinine and protein/creatinine ratios must be collected at first void in the morning and kept in the refrigerator until the subject returns them.

CONFIDENTIAL

No use, disclosure or reproduction outside of Omeros without prior written authorization

3. Vital signs including BP, pulse rate, RR and temperature (after at least 5 minutes of rest).
4. Review of AEs and concomitant medications.
5. Confirmation of eGFR using the MDRD formula to assess eligibility.
6. Review of inclusion and exclusion criteria for study eligibility.

Note: Site must obtain and process urine samples prior to Treatment Visit 1.

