10.1.3. Treatment Visit 1 (Day 1, approximately 7 days after Screening Visit 2)

This visit is to confirm eligibility, randomize (Cohort 2 and Cohort 3) subjects, and administer the first dose of study drug. Randomization may occur up to 2 days prior to Treatment Visit 1 if necessary for site logistical reasons provided eligibility has been confirmed. Eligible subjects for Cohort 1 will initiate treatment with OMS721. Eligible subjects for Cohort 2 and Cohort 3 will be randomized by the pharmacist or unblinded drug-designee at the study center. A computer-generated randomization will be created allocating Cohort 2 and Cohort 3 subjects to either OMS721 or vehicle.

Prior to administering the dose of study drug, the following procedures will be performed:

1. Review of AEs and concomitant medications, including corticosteroid dose (if applicable).
2. Vital signs including BP, pulse rate, RR, and temperature (after at least 5 minutes of rest).
3. ECG taken (after at least 5 minutes of rest in the supine position).
4. Laboratory samples will be collected for:
 - Hematology, chemistry, coagulation, cystatin C
 - Urinalysis
 - Serum or urine pregnancy test in women of childbearing potential. If the test result is positive then the subject will be excluded from the study
 - Blood samples for future research
 - Serum PK sample
 - Serum PD sample
 - Serum ADA sample
5. For three days prior to Treatment Visit 1, three once daily first void urine samples for albumin/creatinine and protein/creatinine ratios will be collected and brought for analysis at this visit.

Study drug will be administered by IV infusion over 30 minutes.

After dosing with study drug, the following procedures will be performed:

1. Vital signs including BP, pulse rate, RR, and temperature (after at least 5 minutes of rest) at the following timepoints: 30 minutes, 1 hour.

CONFIDENTIAL

No use, disclosure or reproduction outside of Omeros without prior written authorization

2. ECG taken (after at least 5 minutes of rest in the supine position), to be obtained immediately before the 5-minute, post dose PK sample.
3. Serum PK samples at the following timepoints after end of dosing: 5 minutes, 2 hours, and 24 hours (**Day 2**), 72 hours (**Day 4**).
4. Serum PD sample after the end of dosing: 2 hours.
5. The subject may be discharged after arrangements are made for the collection of PK samples on **Days 2 and 4**.

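### Exclusion criterion 5 sets the ALT/AST limit at 5.0 x ULN in the protocol synopsis and at 3.0 x ULN in Section 8.2, so one of the two liver-safety entry limits is wrong.

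*Protocol*

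**What the plan says.** The protocol prints the exclusion list twice, each time with 17 items.

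- Synopsis (Section 2), exclusion 5: "Have an alanine transaminase (ALT) or aspartate transaminase (AST) > 5.0 x the upper limit of normal".
- Section 8.2, exclusion 5: "Have an ALT or AST > 3.0 x the upper limit of normal".

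The steps that apply the criteria do not name a list. Section 10.1.1 introduces the first screening procedures with "During Screening Visit 1, the procedures listed below will be performed and documented to determine subject eligibility prior to treatment assignment". Section 10.1.2 (Screening Visit 2) asks for "Review of inclusion and exclusion criteria for study eligibility". Section 10.1.3 says "This visit is to confirm eligibility, randomize (Cohort 2 and Cohort 3) subjects, and administer the first dose of study drug". The schedule in Section 19.2 marks the criteria review at both screening visits and at Treatment Visit 1.

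ALT and AST belong to the chemistry panel (Section 12.1.1). That panel is drawn at Screening Visit 1 (Section 10.1.1) and again before the first dose at Treatment Visit 1 (Section 10.1.3).

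The SAP gives no ALT/AST limit. Its Section 10 plans a listing of subjects who failed any entry criterion.

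**The concern.** The two lists are plainly meant to be the same list: the items and their numbering correspond, and the other 16 agree in substance. Only item 5 carries a different number. It is a liver-safety limit in a trial whose primary objective is safety, judged in part by laboratory tests (Section 6.1).

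Two things are at stake. First, a site working from the synopsis could admit a subject whom Section 8.2 excludes. Section 16.2.3 requires protocol violations to be reported to the sponsor and the local IRB/IEC, and whether this enrolment counts as one depends on the limit. Second, the programmer who builds the SAP listing of eligibility failures has no single value to code for this criterion.

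**Working it through.** No arithmetic applies, because the documents give no ALT/AST distribution. The check is a comparison of the two texts and a search for anything that reconciles them.

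**Step 1. Apply each limit to every possible screening value.** Let x be the higher of ALT and AST, each expressed as a multiple of its upper limit of normal.

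| x | Synopsis exclusion 5 (> 5.0) | Section 8.2 exclusion 5 (> 3.0) | Do they agree? |
|---|---|---|---|
| 3.0 or below | not excluded | not excluded | yes |
| above 3.0, up to and including 5.0 | not excluded | excluded | no |
| above 5.0 | excluded | excluded | yes |

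The conflict is confined to the middle band.

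**Step 2. Look for a reason that the two could both be right.** Neither version is restricted to a cohort, a region or a visit. Neither is redacted, and neither comes from a summary of changes.

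**Step 3. Look for a rule that resolves it.** Neither document says whether the synopsis or the body prevails. Sections 10.1.1 to 10.1.3 and 19.2 refer to the criteria only in general terms, and the SAP is silent on the limit.

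**Step 4. Find which single limit satisfies both texts.** A subject admitted under > 3.0 has x at or below 3.0 and so breaches neither text. A subject admitted under > 5.0 may have x in the middle band and so breach Section 8.2. Only > 3.0 satisfies both.

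**Step 5. Trace what depends on the limit.**

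- SAP Section 8.3.2: the safety population is defined by receipt of study drug, so it does not change.
- SAP Section 8.3.3: the efficacy population is defined by dosing plus baseline and post-baseline 24-hour urine protein, so it does not change.
- Protocol Section 13.1: the sample size is empirical and there is no power calculation. SAP Section 12.3 plans no formal tests. No sample size or error rate changes.
- SAP Section 10: the listing of eligibility failures does change, because membership for a middle-band subject follows from the limit chosen.

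**Step 6. Find where affected subjects would show up.** Exclusion 5 names no visit, whereas exclusions 9 and 10 name Screening Visit 1. Two pre-dose chemistry samples exist. Subjects moved from Cohort 2 screening into Cohort 3 may have a screening period of up to 90 days with no repeat of screening chemistry (Section 10.1.1), so their Screening Visit 1 value may be old by the time of dosing. Screening Visit 1 alone may therefore not give the definitive count, and both samples need to be read.

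**The case against.** The strongest reply is that the two texts can be obeyed together. Exclusions are cumulative: the synopsis excludes values above 5.0 but does not say that values up to 5.0 must be admitted. Section 8.2 also opens with an operative instruction to exclude for any listed reason, while the synopsis has only a heading. A site that reads the whole protocol therefore has one compliant course, > 3.0 x ULN. This stands, and it is why the interim rule below is > 3.0. It does not remove the error: on that reading the synopsis limit has no function and still needs correcting.

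A second reply is that other criteria cover the risk. Exclusion 9 removes subjects with hepatitis B or C, and exclusion 16 removes those who "Have any condition that the Investigator believes would put the subject at risk from participation". These narrow the gap, but neither sets a transaminase limit.

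Some stronger readings are tempting and should not be drawn.

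- *That the two lists have equal standing.* The matching opening sentences belong to the inclusion lists, "Subjects may be included in the study only if they meet all of the following criteria", and say nothing about the exclusions. On the exclusion side the wording favours Section 8.2, although that is not a stated rule of precedence.
- *That the synopsis figure is the mistake.* The operative wording of Section 8.2 makes this plausible, but nothing in the documents shows which value was intended.
- *That sites used different limits, or that a given number of subjects is affected.* Neither is shown. Any rate of middle-band values would be an assumption. The planned total of about 44 is not a safe denominator either: Cohorts 1 and 2 (16 + 10 = 26 planned) were already under way at this amendment, and the earlier protocol text is not supplied.
- *That the mismatch carries over to rollover.* Section 7.1 says "Subjects have to sign an informed consent and meet the eligibility criteria in order to participate in Cohort 3", but no ALT/AST check specific to rollover is described. Whether one is intended is a separate question, and aligning the two numbers does not depend on it.

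**Conclusion.** The inconsistency is definite: the same criterion carries two limits, nothing in either document reconciles them, and one must be wrong. It should be fixed because it is a safety entry limit and the correction is simple.

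The consequence is limited to subjects with ALT or AST above 3.0 and up to 5.0 x ULN before dosing. For them, compliance of the enrolment and membership of the SAP eligibility-failure listing depend on the limit used. How many there are is unknown and may be zero. A reader might infer a threat to the safety analysis or to the comparison with vehicle; the documents do not support that, given the population definitions and the descriptive design.

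The conclusion rests only on the two printed limits and the absence of a precedence rule. It needs no assumption about how common raised transaminases are.

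**What to change.** 1. The sponsor confirms the intended limit and states it in both synopsis exclusion 5 and Section 8.2 exclusion 5 in the next amendment.
2. Until then, sites are told to apply > 3.0 x ULN.
3. The confirmed value is the one programmed for the eligibility-failure listing in SAP Section 10.
4. Subjects already enrolled with a pre-dose ALT or AST above 3.0 and up to 5.0 x ULN, at Screening Visit 1 or Treatment Visit 1, are flagged from data already collected.

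The drafting is one number in one of two places, and no new data are needed. The real costs are IRB/IEC approval of the amendment before it takes effect (Section 16.1), across approximately 15 sites, and the possible loss of a few otherwise eligible subjects while 3.0 applies, or for good if it is the value kept. Carrying the correction in the next amendment, rather than a separate one, keeps the first cost low.
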